4.1.3 Randomization of Subjects

In general, a sample consists of the sampling units chosen from the population eligible to be included. The sampling unit is the unit around which the sampling procedure is planned, and in this study, the unit will be defined as the individual. The sampling frame is the list of all the sampling units in the population. A list of all residential telephone numbers that are publicly listed will be used in this study. This phone list is sorted by area code, and includes phone, name and address information for roughly 6,700 households. Based on the most recent aggregate data from Canada Post, this represents 85.3% (6,700/7,856) of households in Port Colborne. The sampling method is the way in which the sampling units are chosen from the sampling frame. As described above, the sampling method for this study will be a stratified random sampling approach. For stratification, the sampling frame will be divided into five geographic areas categorized by level of exposure to the CoCs. By assigning a random number to each telephone listing within each stratum and then sorting these listings by this random number, the sorted listings can be used to randomly select households for inclusion in the study. Within each household, participants will be randomly selected taking into account the number of residents. Specifically, for a household with r residents, the k th oldest resident will be chosen where k is a random number between 1 and r . The telephone interviewers will be supplied with tables of random numbers for households ranging from sizes of 2 to 10 to select a value for k .

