6.1.1 Power calculations for the health questionnaire

Power was calculated based on the primary objective of the study which is to characterize the current health of residents in Port Colborne using a comprehensive health assessment questionnaire and medical testing. As mentioned previously, a stratified sampling strategy will be applied to recruit individuals from five geographical areas. The sample size of the Health questionnaire and medical tests was calculated by determining the number of individuals needed to measure the prevalence of selected health conditions with sufficient precision both within the Rodney Street Area, and the remainder of Port Colborne. Specifically, the sample size of 1,000 was selected to ensure that a 5% prevalence of asthma could be measured within an accuracy of 2% 16 times out of 20, and that the prevalence of nickel sensitivity estimated at 9.5% among women could be measured within 7% and 13% 16 times out of 20 (see Table 1 below).

Table 1: Sample Size Needed to Compare Disease Prevalence Rates (Proportions)

Health Condition	Anticipated Prevalence	Prevalence Range Permitted**	Subjects needed in Area 3	Subjects needed in remainder of Port Colborne	Minimally detectable Odds Ratio*
Asthma	5%	4-6%	418	777	2.0
Asthma	5%	3-7%	160	193	3.2
Asthma	5%	4.5%-5.5%	699	2662	1.7
Cancer	0.5%	0.4-0.6%	811	5630	3.4
Nickel Sensitivity (females)	9.5%	8%-11%	370	607	1.8
Nickel Sensitivity (females)	9.5%	7%-13%	181	223	2.4

* Comparison of prevalence of disease between Area 3 and the rest of Port Colborne

**with Power of 80% and an alpha error of 5%

Assuming that there is a response rate of 65%, and that 50% of residents in the region are female, there will be 234 female participants in the Rodney Street area and a remaining 251 female subjects in the rest of Port Colborne. This will enable nickel sensitivity to be measured with sufficient precision as outlined in the table above. Moreover, when supplemented with data obtained from males, there will be sufficient precision to measure the prevalence of asthma within an accuracy of 2% in both sexes (see Table 1). It is important to note that due to the rarity of cancer, the health questionnaire is unable to measure the prevalence of cancer in Port Colborne with sufficient precision. The evaluation of this health outcome will be addressed in a subsequent research protocol.

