The estimated number of dwellings and individuals that make up the target population are listed in Table 1. This list is considered approximate as it is based on Canadian census data obtained in 1996.

Table 2: Estimated Number of Households and Individuals 12 years of Age and Older* within Each Sampling Region for the health questionnaire.

Region (EA's)	Number of private dwellings	Estimated population 12 years of age and older
1- West of the Welland Canal, south of Clarence and Augustine Road (151-156)	1,945	4,055
2- West of the Welland Canal, north of Clarence (116-120)	2,260	4,798
3- East of the Canal, south of Durham (includes Durham) and is bounded by Davis and Lake (110)	365	719
4 - East of the Canal, north of Durham (excludes Durham) and is bounded by Snider Road (106,108)	775	2,346
5- Other areas of Port Colborne (101-105,107,109,112-113)	2,030	4,437
Total	7,375	16,355

* assumes that 85% of the Port Colborne community is 12 years of age and older (based on 1996 Census data from Statistics Canada).

It is very important to note that while there are sufficient numbers to measure the prevalence of the selected health conditions with the desired precision, there is limited power to make comparisons between rates in the Rodney Street area to the remainder of Port Colborne. Specifically, with 500 subjects recruited in both the Rodney Street area and other parts of Port Colborne, the study has the power to detect an odds ratio of 2.1 for the comparison of asthma rates between the two regions with a power of 80% and a type I error rate of 5%. The odds ratio of 2.1 corresponds to a greater than two-fold increased prevalence rate in area 3 relative to the rest of Port Colborne. Similarly, for a comparison of nickel sensitivity rates in females between the two regions, there is power to detect an odds ratio of 2.2.

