10.3.3 Instructions Specific to T.R.U.E., Given Post-Application, before Subject Departs

Appendix 10.1: Health Questionnaire

CHAP Health Questionnaire

-  indicates that the questions were derived from the HRQOL-4
 -  indicates that the questions were derived from the 2000 CCHS
 -  indicates that the questions were derived from the Smith-Sivertsen paper
- ADULT indicates adult specific
CHILD indicates child specific

The following information will be kept strictly confidential. Any information that can identify you or your family will be replaced with a unique number (as viewed at the top of this page). This identifying information will be kept separately and under restricted access.

Last Name:  _____

First Name:  _____

Middle Name: _____

Current or Former Resident: **Current / Former**

Number of People in your Household: _____

ALL MEMBERS OF HOUSEHOLD (12+) ARE TO ANSWER THE FOLLOWING QUESTIONS. SOME QUESTIONS MAY NOT APPLY (CHILD OR ADULT SPECIFIC).

Demographic Information

1. What is your date of birth? DD/MM/YYYY 

2. Please indicate your sex: 
 - Male
 - Female

3. People living in Canada come from many different cultural and racial backgrounds.
Are you: 

INTERVIEWER: Read categories to respondent. Mark all that apply.

- 1 ...White?
 - 2 ...Chinese?
 - 3 ...South Asian (e.g., East Indian, Pakistani, Sri Lankan, etc.)?
 - 4 ...Black?
 - 5 ...Filipino?
 - 6 ...Latin American?
 - 7 ...Southeast Asian (e.g., Cambodian, Indonesian, Laotian, Vietnamese, etc.)?
 - 8 ...Arab?
 - 9 ...West Asian (e.g., Afghan, Iranian, etc.)?
 - 10 ...Japanese?
 - 11 ...Korean?
 - 12 ...Aboriginal Peoples of North America (North American Indian, Métis, Inuit / Eskimo)?
 - 13 Other – Specify
-
4. How tall are you without shoes on?  (offer both ways of measuring, want metres)

 5. How much do you weigh?  (offer both ways of measuring, want kg)

6. Do you consider yourself: 
- overweight?
 - underweight?
 - just about right?
7. What is your current marital status?  ADULT
- Married
 - Living Common-law
 - Widowed
 - Separated
 - Divorced
 - Single (never married)
8. Highest grade of elementary or high school completed: 
- ___ Grade 8 or lower (Quebec: Secondary II or lower)
 - ___ Grade 9 – 10 (Quebec: Secondary III or IV; Newfoundland: 1st year of secondary)
 - ___ Grade 11 – 13 (Quebec: Secondary V; Newfoundland: 2nd to 4th year of secondary)
9. Highest degree, certificate or diploma:  ADULT
- ___ No postsecondary degree, certificate or diploma

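### Section 6.1.1 counts on about 467 to 500 Rodney Street participants, but one person per listed household in an area of 365 dwellings yields about 200 to 240

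*Protocol*

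**What the plan says.** Section 4.1.3 takes publicly listed residential telephone numbers as the frame and states that "this represents 85.3% (6,700/7,856) of households in Port Colborne". Households are drawn at random within each stratum, and then one person is chosen: "for a household with r residents, the k th oldest resident will be chosen where k is a random number between 1 and r".

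Table 2 in section 6.1.1 gives Area 3, the Rodney Street area, 365 private dwellings and an estimated 719 people aged 12 or over. The same section, "Assuming that there is a response rate of 65%, and that 50% of residents in the region are female", concludes that "there will be 234 female participants in the Rodney Street area and a remaining 251 female subjects in the rest of Port Colborne", and treats this as enough for nickel sensitivity and, once males are added, for asthma. It then gives a detectable odds ratio of 2.1 for asthma "with 500 subjects recruited in both the Rodney Street area and other parts of Port Colborne", and of 2.2 for nickel sensitivity in women, at 80% power and 5% type I error.

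The header of the questionnaire in Appendix 10.1 carries a different household rule: "ALL MEMBERS OF HOUSEHOLD (12+) ARE TO ANSWER THE FOLLOWING QUESTIONS".

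**The concern.** If one person is taken per household, the number of participants in an area cannot exceed its number of households. Both Area 3 counts used in section 6.1.1 do exceed it. They look as if they were derived from the resident count, while the sampling rule works on households.

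Three statements depend on these counts: the nickel precision in women, which is one of the two reasons given for choosing 1,000; the detectable odds ratios of 2.1 and 2.2; and the near-equal split between Area 3 and the rest. Section 6.4 names Area 3 against the rest of the city as the comparison of particular interest. Selection and allocation cannot be repaired after recruitment, and field staff cannot follow both the rule in section 4.1.3 and the questionnaire header.

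**Working it through.** **Inputs.** Area 3 has 365 dwellings and 719 people aged 12+ (Table 2). Listing coverage is 85.3%, city-wide (4.1.3). Response is 65% and half are female (6.1.1). Prevalences are 5% for asthma and 9.5% for nickel sensitivity in women (Table 1). The precision criterion is 16 times out of 20, i.e. 80% confidence, z = 1.2816. The test is taken as two-sided, since the protocol does not say.

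**1. The plan's headcount.** 719 x 0.65 x 0.50 = 233.7, the stated 234. For both sexes, 719 x 0.65 = 467. So the response rate was applied to every resident aged 12+.

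**2. Feasibility with one person per household.** 365 x 0.853 = 311 listed households.
- 467 / 311 = 150% response needed from listed households.
- 500 / 365 = 137% response needed even if every dwelling were listed.
- Even with every resident approached, 500 / 719 = 70%, above the assumed 65%.

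**3. Expected yield.**
- 85.3% listed: 365 x 0.853 x 0.65 = 202, about 101 women.
- All listed: 365 x 0.65 = 237, about 119 women.
- All residents aged 12+ of listed households invited: 719 x 0.853 x 0.65 = 399.

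**4. Precision in Area 3.** Required size is n = n0 / (1 + n0/N), with n0 = z² p(1-p) / d². Half-width is z sqrt(p(1-p)/n) sqrt(1 - n/N).
- Asthma, d = 0.02: n0 = 195. N = 900 reproduces Table 1's 160, and N = 719 gives 153. At n = 202 and N = 719 the half-width is 1.7 points. The target is met.
- Nickel in women, d = 0.025: n0 = 226. N = 900 reproduces Table 1's 181. With 719 / 2 = about 360 women, the requirement is 226 / (1 + 226/360) = 139. At 101 women the half-width is 1.2816 x sqrt(0.095 x 0.905 / 101) x sqrt(1 - 101/360) = 3.2 points; at 119 it is 2.8. The permitted range of 7% to 13% leaves 2.5 points below 9.5%. The target is missed.

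**5. Detectable odds ratios.** With p1 in Area 3, p0 elsewhere, k = n2/n1 and pbar = (p1 + k p0)/(1 + k):

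n1 = [1.96 sqrt(pbar(1-pbar)(1+1/k)) + 0.84 sqrt(p1(1-p1) + p0(1-p0)/k)]² / (p1-p0)²

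The continuity correction multiplies this by (1/4)[1 + sqrt(1 + 2(1+1/k)/(n1(p1-p0)))]². I solved for the odds ratio at 80% power, and used the same corrected formula for power.

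| Outcome | Area 3 v rest | Detectable OR | Power at stated OR of 2.1 |
|---|---|---|---|
| Asthma (plan) | 500 v 500 | 2.07 (stated 2.1) | 82% |
| Asthma | 202 v 500 | 2.48 | 60% |
| Asthma | 202 v 798 | 2.35 | 67% |
| Asthma | 237 v 763 | 2.26 | 71% |
| Nickel, women (plan) | 234 v 251 | 2.20 (stated 2.2) | |
| Nickel, women | 101 v 251 | 2.65 | |
| Nickel, women | 101 v 399 | 2.50 | |
| Nickel, women | 119 v 381 | 2.40 (rounded up from 2.39) | |

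The rows with 798, 763, 399 and 381 assume that the places Area 3 cannot fill go to the other areas, keeping the total at 1,000 (500 women).

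**The case against.** Several points on the other side stand and limit the finding.

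- **The design does not fail as a whole.** A reader might infer that all the stated precision is lost. It is not: asthma within 2 points in Area 3 survives, with 202 against 160 needed.
- **The nickel gap is smaller than it first looks.** Setting 101 women against Table 1's 181 overstates it, because 181 rests on a population of 900; about 360 women gives 139. Quoting a 95% half-width against the plan's 80% criterion would also be unfair. At 101 women the 80% interval is about 6.3% to 12.7%, outside only the lower limit of 7%.
- **The tabulated sensitivity is nearly kept.** The Table 1 rows used to choose 1,000 list odds ratios of 3.2 for asthma and 2.4 for nickel. Asthma at 2.3 to 2.5 is better than its row; nickel at 2.4 to 2.65 is equal or slightly worse.
- **Limited power is conceded.** Section 6.1.1 says so for the area comparison, and section 2.0 puts characterisation first. But the 2.1 and 2.2 quoted with that concession still rest on an unattainable count.
- **The dwelling count is approximate.** It comes from the 1996 census. Scaling to the 7,856 households in section 4.1.3 gives 365 x 7,856 / 7,375 = 389, and 389 x 0.853 x 0.65 = 216 participants. The ceiling moves a little but stays well below 467.

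The questionnaire header is a form instruction, not a sampling rule, so it does not rescue the counts. If it did govern, about 399 would result, still short of 467. Replacing drop-outs (4.1.1.2) cannot lift the number above the number of households.

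**Conclusion.** Wrong as written. The Area 3 counts in section 6.1.1 contradict the household rule in section 4.1.3, and this holds at any response rate or listing coverage. The expected size, about 200 to 240 people and 100 to 120 women, is less certain: it assumes that 65% response and 85% to 100% listing apply in Area 3, for which no coverage is documented.

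On that basis the nickel precision in women is missed modestly. The detectable odds ratios rise from the stated 2.1 to about 2.3 to 2.5 for asthma, and from 2.2 to about 2.4 to 2.65 for nickel. Power at the stated asthma odds ratio falls from 82% to about 60% to 71%. The asthma precision claim for Area 3 stands.

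**What to change.** Choose one within-household rule and make section 4.1.3, section 6.1.1 and the questionnaire header agree.

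- **(a) Keep one person per household.** State an Area 3 size of about 200 to 240 (100 to 120 women), with the listing and response assumptions. Move the places that cannot be filled to Areas 1, 2, 4 and 5. Replace the 234/251 and 500/500 counts, the odds ratios of 2.1 and 2.2, and the nickel-precision statement with recomputed values, using the Table 2 population for the finite-population correction.
- **(b) Invite every resident aged 12+ in contacted Area 3 households.** State about 400, which is still below 467 to 500, and use variances that allow for clustering within households.

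The cost is protocol wording and less favourable stated figures, plus a cluster term in the analysis under (b). Neither option raises the total of 1,000.

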6.2 Outcome measures

6.2.1 Health questionnaire

The CHAP health questionnaire provides self-reported data within five categories: demographics, exposure, health related quality-of-life, current medical health status, and mental health.

6.2.1.1 Demographics

The demographic information collected will include: date of birth (from which age can be calculated), sex, race, height and weight (from which body mass index can be calculated), household size, marital status, education, and income. This information will be used to adjust the data if the sample distribution is different than that of the real or true distribution in the population. Thus, it is important in assessing whether a representative sample has been drawn. This data can also be used to adjust for differences when comparing to provincial or normative data.

6.2.1.2 Exposure

The exposure information collected falls into five categories: residential, occupational, lifestyle/dietary, educational, and other exposure. The residential information will include address, period of stay, type of dwelling, and age of residence. From this, information on the number of years of residency in Port Colborne can be calculated. There is a child specific section that collects information on children who have had more than one permanent address. Residential information will also be used to assign exposure to CoCs

into two categories. Specifically, exposed which equates to the Rodney Street area versus non-exposed which equates to all other geographical locations within Port Colborne. Occupational exposure is assessed for specific high exposure industries. Details are collected for job description, activity, and duration of employment. Lifestyle/dietary exposure includes information collected on the source of drinking water, gardening, high exposure non-occupational hobbies, smoking, second-hand smoke, and alcohol consumption. Education exposure is specific to children; the questionnaire is designed to collect information about schools attended and the duration of attendance. Other exposure information collected includes data on jewellery that pierces the skin.

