3.2.1.1.2 Qualitative exposure

A vital goal of the questionnaire is to obtain general exposure information and to determine if a relationship exists between such exposure and potential health issues. “Exposure” refers to “total exposure,” and thus includes both exposure related to residential and occupational sources (e.g. where you have lived and worked and for how long, nature of the job), as well as other secondary sources, such as diet and lifestyle (e.g. water sources, hobbies). Accordingly, detailed questions are included that encompass these areas to gauge both current and past individual exposure.

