3.3 Confounders

“A confounder is a variable that (a) is causally related to the disease or condition under study independently of the exposure of interest or, as often occurs in practice, serves as a proxy measure for unknown or unmeasured causes, and (b) is associated with the exposure under study in the study population, but is not a consequence of this exposure. It

follows from (a) that within each level of the exposure under study, the confounder is related to the disease conditional on exposure level” (Kelsey et al., 1996). An example of confounding may better explain this phenomenon. Consider a study of cigarette smoking and lung cancer. Many factors that are related to cigarette smoking are independently related to lung cancer. For example, age is strongly associated with lung cancer, with the incidence rates of this cancer much higher among those 65 years of age and older. To assess the association between cigarette smoking and lung cancer, one must control for the effects of this potential confounder. If controlling for this factor does not affect the association between smoking and lung cancer, then there is little or no confounding effect present.

Two methods are used for controlling for confounding in cross-sectional studies: matching in the study design or adjustment in the analyses of the data. Matching is rarely used in cross-sectional studies for two reasons. First, these types of studies are often conducted in general population groups where information on potential confounding variables on individual participants is not known prior to sample selection. Second, information on the level of exposure is frequently unavailable at the outset of the study, so it is not feasible to divide subjects into groups based on levels of exposure for the purposes of matching. In this study, the only exposure information known in advance to sample selection is the current location of residence. This information will not be used for matching, but will be used in the sampling strategy where individuals will be grouped according to predefined boundaries of exposure.

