3.4 Study Limitations

Many factors can influence health and confound the measures of health including: age, gender, family history, as well as social, physical and economic environment. These have been taken into account in the CHAP project wherever possible. There has been the addition of the three confounding metals, lead, mercury and cadmium. We will be able to determine the levels of CoCs in the body but where there is the presence of multiple chemicals, it may be difficult to deduce any association with one particular contaminant. In evaluating the exposure and levels of CoCs in the body, it should be noted that the exposure does not indicate the level of lifetime exposure or the highest exposure that an individual has had. The level of CoCs detected in the body measure the level of metal at that moment of time. The measures will not be able to differentiate between recent exposure or levels of metal from a previous or historical exposure, in addition the measures will not be a reflection of the highest exposure or the duration of the exposure. The tests for CoCs will only measure the presence of CoCs and not the end organ effect of the CoCs.

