The logistic regression model will provide a parameter estimate that can be readily transformed into an odds ratio. This odds ratio provides a measure of risk that can be used to determine whether those with high levels of exposure to CoCs are more likely to have a specified health condition. Survey participants will be categorized into tertiles based on their clinical exposure measurements and into binary groups based on the answers they give to the exposure question in the health questionnaire. Risk estimates will be calculated by comparing the prevalence of disease among those in the highest tertile of exposure to those in the lowest and for those indicating exposure in their answers to the questionnaire versus no exposure. The 95% confidence intervals for these odds ratios will also be calculated. This confidence interval can be used to determine whether or not the association may be due to chance. These estimates of risk will be adjusted for the potential confounding influence of other relevant variables, such as age, sex, smoking habits, alcohol use, and indicators of socio-economic status. All statistical analyses will be conducted by using SAS. The fit of the model will be assessed by using the Hosmer-Lemeshow goodness of fit statistic.

Multivariate analysis of variance will be used to compare laboratory measures of CoCs taken in Port Colborne residents to a normative sample. These multivariate models will be adjusted by age and sex of the subjects. Differences between the two populations will be evaluated by using the F-test statistics generated from the ANOVA model. Where necessary, measured levels of CoCs will be transformed in order to ensure that assumptions of normality are satisfied. If this assumption cannot be met through a

transformation, than non-parametric methods (e.g., Wilcoxon Rank Sum test) will be considered.

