 - ___ Trades certificate or diploma from a vocational school or apprenticeship training
 - ___ Non-university certificate or diploma from a community college, CEGEP, school of nursing, etc.
 - ___ University certificate below bachelor's level
 - ___ Bachelor's degree
 - ___ University certificate or diploma above bachelor's degree

10. Can you estimate in which of the following groups your household income falls? 

ADULT

Was the total household income ...

- Less than \$20, 000?
 - Less than \$10, 000?
 - Less than \$5, 000?
 - \$5, 000 or more?
 - \$10, 000 or more?
 - Less than \$15, 000?
 - \$15, 000 or more?
- \$20, 000 or more?
 - Less than \$40, 000?
 - Less than \$30, 000?
 - \$30, 000 or more?
 - \$40, 000 or more?
 - Less than \$50, 000?
 - \$50, 000 to less than \$60, 000?
 - \$60, 000 to less than \$80,000?
 - \$80, 000 or more?
- No Income

Residential Information

11. Please fill in the following table for your current and all past residences in Port Colborne.

Address ¹	Period of Stay ²		Type of Dwelling ³	Age of Residence ⁴
	From	To		

¹Please indicate street address, city, province, country, and postal code.

²Please indicate from MM/YYYY to MM/YYYY.

³Please indicate one of the following:

- Single Detached House
- Semi-Detached or Double (side-by-side)
- Garden House, Town-House or Row House
- Duplex (one above the other)
- Low-rise apartment (less than 5 stories)
- High-rise apartment (5 or more stories)
- Institution
- Collective dwelling (such as a Hotel/Motel, Rooming or Boarding House)
- Mobile home
- Farm or Acreage
- Other (please specify _____)

⁴Please indicate number of years.

12. If you have resided or are residing in more than one home concurrently, please fill in the following table: CHILD

Address	Percentage of Time Spent
#1	
#2	

Occupational Information

13. a) Do you now or have you ever worked in one of the following industries/occupations: Y/N ADULT.

b) If yes, please specify which industry/occupation:

- | | |
|--------------------------------|-----------------------------------|
| 1 - Underground mining | 8 - Welding |
| 2 - Smelting | 9 - Brazing |
| 3 - Metal Refining | 10 - Sintering |
| 4 - Foundry work | 11 - Plumbing |
| 5 - Steelmaking | 12 - Metal plating/electroplating |
| 6 - Metal Cutting and grinding | 13 - Shipbuilding/breaking |
| 7 - Boiler maker/repairer | 14 - Lumberyard/Sawmill |

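### Residential exposure is a two-level area label with no duration or past-address rule, although every dated Port Colborne address is collected

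*Protocol*

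**What the plan says.** **The rule.** Protocol section 6.2.1.2 uses residential information to place participants in two exposure categories: "exposed which equates to the Rodney Street area versus non-exposed which equates to all other geographical locations within Port Colborne". It sets no minimum stay, time window or past-address rule. In section 6.4 the logistic models put participants "into binary groups based on the answers they give to the exposure question in the health questionnaire".

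**The data.** Section 6.2.1.2 also states: "The residential information will include address, period of stay, type of dwelling, and age of residence". Item 11 under Residential Information in Appendix 10.1 reads: "Please fill in the following table for your current and all past residences in Port Colborne". It asks for the month and year of the start and end of each stay.

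**What is derived from the data.** Section 6.2.1.2 says that "information on the number of years of residency in Port Colborne can be calculated". This variable appears once in the mock tables, as a descriptive row of Table 3. Time lived in Area 3 is not derived anywhere.

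**The stated purpose.** Section 3.2.1.1.2 counts where a person has lived, and for how long, as part of exposure. It says the questions are there "to gauge both current and past individual exposure".

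**The other exposure measure.** Section 3.4 says of the metal measurements: "The measures will not be able to differentiate between recent exposure or levels of metal from a previous or historical exposure". It adds that they do not reflect how long exposure lasted.

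**The concern.** Many of the outcomes build up over time. The questionnaire asks about long-term diagnosed conditions, and section 3.2.2.3.2 describes nickel and cobalt sensitisation as following chronic exposure and probably lasting for life. For such outcomes, someone who moved to Area 3 last month and someone who has lived there for thirty years are different exposures, but the label treats them alike. Years in Port Colborne as a whole do not help, because twenty years in Area 3 and twenty years in the rural stratum give the same value.

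If mislabelling is unrelated to disease, it pulls the odds ratio for Area 3 versus the rest towards 1. Section 6.1.1 already warns that power for this comparison is limited, so there is little to spare. The metal measurements cannot fill the gap by the protocol's own account. Item 11 is then the main source of residential history, and the stated rule reduces it to one binary label.

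**Working it through.** **1. Who is mislabelled under each reading.** Section 6.2.1.2 does not say whether the label uses current address or any address ever held.

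- *Current address.* Newcomers to Area 3 are exposed. Former Area 3 residents living elsewhere in the city are non-exposed.
- *Ever lived there.* Newcomers are still exposed, because there is no duration rule. Former residents are also exposed.

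The newcomer problem holds under both readings; the former-resident problem holds only under the first. Two places support the first reading: section 3.3 says that "the only exposure information known in advance to sample selection is the current location of residence", and the internal-comparison mock tables set Area 3 against Areas 1, 2, 4 and 5 by sampling area. Former residents here means people still living in Port Colborne, since section 4.1.1.1.1 requires that.

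**2. The protocol's own figures.** Section 6.1.1 gives detectable odds ratios of 2.1 for asthma (5% prevalence, 500 versus 500) and 2.2 for nickel sensitivity in women (9.5%; I take 250 versus 250), with 80% power and alpha 5%, taken as two-sided.

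Power = Φ{[|p₁ − p₀| − ½(1/n₁ + 1/n₀) − 1.96·se₀] / se₁}, where se₀ is the pooled and se₁ the unpooled standard error. The middle term is the continuity correction.

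- Asthma: detectable odds ratio 2.07 with the correction, 2.02 without.
- Nickel: 2.17 with, 2.11 without.

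The corrected values round to the stated 2.1 and 2.2, so the correction is used below. Both figures assume that the area label equals true exposure.

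**3. Illustration of dilution.** Let *a* be the share of the Area 3 group that is effectively unexposed (newcomers) and *b* the share of the other group that is effectively exposed (former Area 3 residents). For asthma:

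- p₀ = 0.05
- p₁ = 2.1 × 0.05 / (0.95 + 2.1 × 0.05) = 0.105 / 1.055 = 0.0995
- observed prevalence in Area 3 = (1 − a)·p₁ + a·p₀
- observed prevalence elsewhere = (1 − b)·p₀ + b·p₁

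Worked case, a = 20%, b = 5%: Area 3 = 0.8 × 0.0995 + 0.2 × 0.05 = 0.0896; elsewhere = 0.95 × 0.05 + 0.05 × 0.0995 = 0.0525; odds ratio = (0.0896/0.9104) / (0.0525/0.9475) ≈ 1.78.

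| a | b | Asthma OR | Power | Nickel OR (women) | Power |
|---|---|---|---|---|---|
| 0 | 0 | 2.10 | 82% | 2.20 | 81% |
| 10% | 0 | 1.98 | 74% | 2.07 | 74% |
| 20% | 0 | 1.87 | 65% | 1.94 | 64% |
| 20% | 5% | 1.78 | 58% | 1.84 | 57% |

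Without the continuity correction, asthma power in the four rows is 85%, 78%, 69% and 63%.

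**4. How plausible is b?** Table 2 in section 6.1.1 gives 719 people aged 12 or older in Area 3 and 16,355 in the city, so 15,636 elsewhere. b = 5% implies 0.05 × 15,636 ≈ 782 former Area 3 residents, more than the area's present population. Decades of turnover could produce that, but nothing in the document shows it. The rows with b = 0 need no such assumption.

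**The case against.** - **Detail for an analysis plan.** How a covariate is coded is often settled later, and section 6.4 does refer to a series of questionnaire exposure variables and a summary measure. That would answer a complaint of missing detail. Here, however, section 6.2.1.2 states the two-level rule and section 6.4 makes the questionnaire exposure binary.
- **Former residents.** A reader might infer that the plan definitely counts them as non-exposed. The text does not support that: it never says current address, and an ever-lived rule would also be binary and would fit the wording. This half of the point must stay conditional.
- **Disclosure and purpose.** Section 3.4 admits that lifetime exposure is not captured and lists limits of the exposure data. The primary objective is to describe current health, and the area contrast is not what set the sample size. This lowers the weight of the point. It does not explain leaving dated addresses unused.
- **Newcomers may not be unexposed.** Section 1.0 describes contamination over a wide area of the city, so a person moving into Area 3 from another part may carry some exposure. Current location is also a fair index for a comparison of communities. Both stand, and treating newcomers as wholly unexposed makes the illustration more severe.
- **Duration is imperfect.** Years of residence rise with age. The asthma items record no age at diagnosis and patch-test sensitisation has no onset date, so time before and after onset would be mixed. This stands and shapes the fix.

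**Conclusion.** The point holds as an inexpensive improvement on a stated rule. Section 6.2.1.2 labels recent arrivals in Area 3 as exposed whichever address is meant. It labels former Area 3 residents as non-exposed only if current address is meant, which is likely but not stated.

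The size is unknown. With newcomers alone mislabelled at 10% to 20%, a true asthma odds ratio of 2.1 would appear as about 1.98 to 1.87; adding 5% former residents gives 1.78, with power about 58% against 82%. These figures rest on assumed mobility, on newcomers having no relevant exposure, and on mislabelling unrelated to disease.

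A reader might infer that the study is shown to lose this much power, or that the area comparison is invalid. Neither follows: the documents give no mobility rate, and current area remains a legitimate contrast between communities. What it does not measure is residential exposure history.

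**What to change.** 1. In section 6.2.1.2, state which address the two-level label uses.
2. Code each address from item 11 to its stratum before identifying information is removed (section 4.2.2.1 places removal before any analysis).
3. Derive ever/never lived in Area 3, and years in Area 3 as none, below the median, or above the median.
4. Fit these as additional residential exposure variables in the age- and sex-adjusted logistic models of section 6.4. Keep the current-area contrast as planned.
5. Where age at diagnosis is recorded, count only years in Area 3 before diagnosis. Set a comparable age cut-off for participants without the condition, since otherwise only the cases' exposure time is shortened. State that asthma and patch-test sensitisation have no onset date, so their results use years up to interview.

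The cost is some address coding and a few derived variables, with no new questions or participants. The drawbacks are reliance on recalled dates and the correlation of duration with age, which makes careful age adjustment necessary and will widen the intervals.
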